3.3.1.1 Measurable disease

Measurable disease will be defined as the presence of at least one measurable nodal or non-nodal lesion. If the measurable disease is restricted to a solitary lesion, its neoplastic nature should be confirmed by cytology/histology. For more details on nodal and non-nodal lesion, refer protocol Section 14.2.4.

3.3.1.2 Responder

A patient will be called a responder if at any post baseline visit, patient is assessed to have response (PR and higher) and if the response is confirmed atleast 4 weeks apart.

3.3.1.3 Non Responder

A patient will be called a non-responder if at any baseline visit, patient is assessed to have no response (unconfirmed response of CR/PR or response of SD, PD). A patient who discontinues for any reason before the data cut-off date of the CSR without a confirmed assessment of response will be considered a non-responder. Patients with unknown or missing response, or who are treated in the study but provide no information on response at the end of treatment will also be treated as non-responders.

The non-responders will be included in the denominator while calculating percentages.

3.3.1.4 Adequate tumor response assessment

An adequate tumor response assessment is considered as disease assessment that is indicating any disease status apart from “unknown” or “not done”.

Date of last adequate tumor assessment is the date the last tumor assessment with overall lesion response of CR, PR or SD which was made before an event or a censoring reason occurred. In this case the last tumor evaluation date at that assessment is used. If no post-baseline assessments are available (before an event or a censoring reason occurred) the date of randomization/start of treatment is used.

The tumor assessment will be time slotted using the time windows displayed in Table 3-4:

Table 3-4 Time windows for tumor assessment

| Time window | Planned Visit Timing | Time Window Definition |
|-------------|----------------------|---------------------------------|
| Week 8 | 57 (week 8) | (1,86] days ; (1, 12] weeks |
| Week 16 | 113 (week 16) | (86, 142] days ; (12, 20] weeks |
| Week 24 | 169 (week 24) | (142, 198] days; (20, 28] weeks |
| Week 32 | 225 (week 32) | (198, 282] days; (28, 36] weeks |

| | | |
|---------------------------|---------------|-------------------------------------|
| Week 40 | 280 (week 40) | (282, 352] days; (36, 44] weeks |
| Week 48 | 337 (week 48) | (282, 380] days; (44, 52] weeks |
| Until week 48 (12 months) | X (week Y) | (X-27, X+29] days; (Y-4, Y+4] weeks |
| Week 60 | 421 (week 60) | (380, 464] days; (54, 66] weeks |
| Week 72 | 505 (week 72) | (464, 548] days; (66, 78] weeks |
| Week k (beyond 12 months) | X (week Y) | (X-43, X+41] days; (Y-6, Y+6] weeks |

3.3.1.5 Confirmation of response

Where a study requires confirmation of response (PR or CR), changes in tumor measurements must be confirmed by repeat assessments that should be performed not less than 4 weeks after the criteria for response are first met.

3.3.1.6 Best Overall Response

The best overall response is the best response recorded from the start of the treatment until disease progression/recurrence (taking as reference for PD the smallest measurements recorded since the treatment started). In general, the patient's best response assignment will depend on the achievement of both measurement and confirmation criteria. BOR will be assessed based on the responses provided by the Investigator on centrally and locally assessed data.

The best overall response will usually be determined from response assessments undertaken while on treatment. Any assessments taken more than 30 days after the last dose of study treatment will not be included in the best overall response derivation. If any alternative cancer therapy is taken while on study any subsequent assessments would ordinarily be excluded from the best overall response determination.

The best overall response for each patient is determined from the sequence of overall (lesion) responses according to the following rules:

- CR = at least two determinations of CR at least 4 weeks apart before progression where confirmation required
- PR = at least two determinations of PR or better at least 4 weeks apart before progression (and not qualifying for a CR) where confirmation required
- SD = at least one SD assessment (or better) >6 weeks after randomization/start of treatment (and not qualifying for CR or PR).
- PD = progression ≤12 weeks after randomization/start of treatment (and not qualifying for CR, PR or SD).
- UNK = all other cases (i.e. not qualifying for confirmed CR or PR and without SD after more than 6 weeks or early progression within the first 12 weeks).

3.4 PK evaluations

The LLOQ for ribociclib (and LEQ803) in plasma is approximately 1.00 ng/mL. The LLOQ for everolimus in whole blood is approximately 0.3 ng/mL. The LLOQ for exemestane in plasma is approximately 0.0200 ng/mL. All concentrations below the LLOQ or missing data will be labeled as such in the concentration data listings.

Only PK concentration data will be summarized for CSR. The PK parameters will be summarized outside of CSR.

3.5 Analysis of the primary objective

The primary objectives of the trial are as follows:

- Phase I**

The primary objective of this dose escalation part of the study is to estimate the MTD(s) and/or RP2D of ribociclib in combination with everolimus and exemestane in postmenopausal women with HR+, HER2 negative advanced breast cancer.

- Phase II**

The primary objective is to evaluate efficacy measured by Clinical benefit rate (CBR) at 24 weeks for the triple combination of ribociclib + everolimus + exemestane among patients with HR+, HER2 negative advanced breast cancer following the progression of CDK 4/6 inhibitors. CBR will be assessed based on the responses provided by the Investigator on centrally and locally assessed data.

3.5.1 Primary end point

3.5.1.1 Phase I

The primary end point for the Phase I, dose escalation part of this study, is the incidence rate of Dose Limiting Toxicities (DLTs) in Cycle 1 (28 day cycle).

3.5.1.2 Phase II

The primary end point of this Phase II part of this trial, is CBR at week 24.

3.5.2 Statistical hypothesis, model, and method of analysis

3.5.2.1 Phase I

MTD definition: The MTD is defined as the highest combination drug dosage not causing medically unacceptable, DLT in more than 33% of the treated patients in the first cycle of treatment. AEs and laboratory abnormalities considered to be DLTs are defined in Protocol Table 6-3. Only one RP2D will be tested in the Phase II.

In the dose escalation a total of 6 patients will be treated at dose-level 1 (cohort A). Patients must complete a minimum of one cycle of treatment with the minimum safety evaluation and

drug exposure or have had a DLT within the first cycle of treatment to be considered evaluable for dose escalation decisions.

- If $\leq 33\%$ of patients experience a DLT in cohort A (dose level 1), the dose will be escalated to the next level cohort B (dose level +1) where 3 patients will be enrolled.
- If $\leq 33\%$ patients experience DLTs in cohort B, additional 3 patients will be treated at the same dose level.
- If $\leq 33\%$ patients experience a DLT in both cohorts, then the optimal treatment dose based on tolerability and safety profile will move into Phase II.
- If $>33\%$ patients experience DLTs in both cohorts, the dose will be de-escalated to the next level down.

Dose escalation and R2PD decisions will be made jointly by Steering Committee members and Novartis study personnel.

Listing and summary tables of DLT starting during the first 28 days of treatment by primary system organ class, preferred term, by dose cohort and overall for Phase I will be presented based on DLT-determining set (DDS).

3.5.2.2 Phase II

- Clinical Benefit Rate (CBR):

Clinical Benefit Rate (CBR) is defined as the proportion of patients with a complete response (CR), partial response (PR), stable disease (SD) or Non-CR Non-PD (NCRNPD) at 24 weeks as per RECIST V1.1. Thus, any instance of CR, PR, SD or NCRNPD in the first 24 weeks of the treatment, without having an instance of progressive disease (PD) will be accounted for, while calculating CBR. The instances of unconfirmed CR and/or PR will also be accounted for, while calculating CBR.

Demonstration of significant Clinical Benefit Rate (CBR) will be based on this study with at least an 80% power to test the null hypothesis that the clinical benefit rate in 24 weeks is at least 10% or less with an alternative hypothesis that this rate is above 10%.

All the other patients will be counted as not having clinical benefit.

The study is designed to test the following statistical hypothesis:

$$H_0 : \text{CBR} \leq 10\% \text{ vs. } H_1 : \text{CBR} > 10\%$$

The null hypothesis will be rejected and successful clinical benefit will be demonstrated if the lower limit of the 95% confidence interval is greater than at least 0.10. Thus, if 8 or more patients show clinical benefit at 24 weeks then the null hypothesis will be rejected and significant clinical benefit will be demonstrated.

To show significant clinical benefit, currently at least ≥ 8 patients will have to achieve CBR at 24 weeks. But if the number of patients enrolled in the study is higher than the planned number of 33 patients (approximately 44 to 46), then the requirement for the number of patients to have achieved CBR will also increase (up to ≥ 10 patients).

CBR will be summarized by frequency and percentage together with the 95% confidence intervals. An exact binomial confidence interval (implemented using SAS procedure FREQ with EXACT statement for one-way tables) will be calculated [Clopper & Pearson, 1934].

CBR will be calculated based on FAS; however, patients with only non-measurable disease at baseline will be included in the numerator if they achieved a complete response.

For primary efficacy variable, the analysis time point is when all patients who are enrolled complete 24 weeks or discontinue from the study earlier. Phase 1 patients who had received the RP2D and are post CDK 4/6 completing 24 weeks or discontinue early will also be included in the final phase II analysis.

When examining clinical benefit, patients with a best overall response assessment of unknown (UNK) will not be regarded as “responders” but may be included in the denominator for CBR calculation.

For the primary analysis, CBR will be assessed based on the centrally assessed tumor responses provided by the Investigator according to RECIST Version 1.1. Additionally, above analysis will be repeated for CBR based on the locally assessed tumor response using full analysis set. Analysis will also be performed using per protocol analysis set, as appropriate.

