3.1 Objectives and related endpoints-Phase I

Table 3-1 Objectives and related endpoints-Phase I

	Objective	Endpoint
PHASE I		
Primary	To determine the maximum tolerated dose (MTD) and/or recommended Phase II dose (RP2D) for the combination of ribociclib + everolimus +exemestane when dosed continuously	Incidence of Dose Limiting Toxicities (DLTs) in Cycle 1 (28 day cycle)
Secondary	To determine the safety and tolerability based on NCI	Incidence and severity of adverse events(AE) and serious

[figure not shown]
	Objective	Endpoint
	Common Terminology for Adverse Events Version 4 when treated with ribociclib + everolimus + exemestane continuously in subjects with HR+ HER2- negative advanced breast cancer.	adverse events (SAE), clinical laboratory values, vital signs and electrocardiogram (ECGs), dose interruptions, reductions and dose intensity.
	To determine the pharmacokinetic (PK) profile of everolimus and ribociclib when dosed continuously in the triplet combination.	PK parameters including, but not limited to, AUC _{0-4h} , C _{trough} , C _{max} , accumulation ratio (Racc).
	To assess the preliminary anti-tumor activity of the triplet combination of ribociclib + everolimus + exemestane when combination is given continuously.	Overall response rate (ORR), Disease Control Rate (DCR), Clinical benefit rate (CBR) based on central assessment per RECIST v1.1, CBR is defined as CR, PR, SD or Non-CR, Non-PD (NCRNPD) lasting 24 weeks or longer.

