3.2 Objectives and related endpoints-phase II

Table 3-2 Objectives and related endpoints-phase II

	Objective	Endpoint
PHASE II		
Primary	Determine the Clinical Benefit Rate (CBR) at 24 weeks amongst patients receiving triple therapy with ribociclib + everolimus + exemestane, for advanced/metastatic HR+, HER2-negative breast cancer following progression on CDK 4/6 inhibitor.	Clinical Benefit Rate (CBR) defined as the proportion of patients with a complete (CR) or partial response (PR), or with stable disease (SD) at 24 weeks as per RECIST 1.1 or Non-CR Non-PD (NCRNPD) at week 24.
Secondary	To determine centrally assessed progression Free Survival (PFS) in HR+ HER2-negative advanced breast cancer.	Progression-free survival (PFS), defined as the time from date of treatment to the date of first documented progression or death due to any cause. If a

Objective	Endpoint
	subject has not had an event, PFS will be censored at the date of last adequate tumor assessment. Disease progression for primary efficacy endpoint derivation will be based on the central radiologist's tumor assessment.
To determine overall response rate (ORR)	Overall response rate (ORR) defined as the proportion of patients whose best overall response is either complete response (CR) or partial response (PR) according to RECIST 1.1.
To determine Overall Survival (OS)	This is defined as the time from treatment initiation with study treatment until death as a result of any cause.
To determine Duration of Overall Response (DOR)	Duration of Overall Response defined as the time between the initial response to the treatment with the combination of ribociclib+everolimus+ exemestane, and subsequent disease progression or recurrence.
To evaluate time to deterioration or ECOG performance status	Time to definitive deterioration of ECOG performance status from baseline.
To determine safety and tolerability	Adverse Events (AEs), serious AE (SAEs), changes in hematology and chemistry values, vital signs, dose interruptions, reductions and dose intensity.
To determine the PK profile of ribociclib and everolimus in the triplet combination	PK parameters including, but not limited to, AUC _{0-4h} , C _{trough} , C _{max} , accumulation ratio (Racc)

4 Study design

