3.7.2.1 ORR, DCR and CBR

- ORR:

Overall response rate (ORR) defined as the proportion of patients who's best overall response is either complete response (CR) or partial response (PR) according to RECIST 1.1. ORR will be calculated based on FAS; however, patients with only non-measurable disease at baseline will be included in the numerator if they achieved a complete response. ORR will be summarized by frequency and percentage. The exact 95% two-sided confidence interval will also be provided.

When examining overall response, patients with a best overall response assessment of unknown (UNK) will not be regarded as “responders” but may be included in the denominator for ORR calculation.

Best overall response for each patient will be listed and summarized on FAS.

- DCR:

Disease control rate (DCR) is the proportion of patients with a best overall response of CR or PR or SD. DCR will be calculated based on FAS; however, patients with only non-measurable disease at baseline will be included in the numerator if they achieved a complete response. DCR will be summarized by frequency and percentage. The exact 95% two-sided confidence interval will also be provided.

When examining disease control, patients with a best overall response assessment of unknown (UNK) will not be regarded as “responders” but may be included in the denominator for DCR calculation.

- CBR:

CBR is defined as the proportion of patients with a CR, PR, SD or NCRNPD as per RECIST V1.1 by week 24. Thus, any instance of CR, PR, SD or NCRNPD in the first 24 weeks of the treatment, without having an instance of PD will be accounted for, while calculating CBR. The instances of unconfirmed CR and/or PR will also be accounted for, while calculating CBR.

CBR will be calculated based on FAS; however, patients with only non-measurable disease at baseline will be included in the numerator if they achieved a complete response. CBR will be summarized by frequency and percentage together with the 95% confidence intervals. An exact binomial confidence interval (implemented using SAS procedure FREQ with EXACT statement for one-way tables) will be calculated [Clopper & Pearson, 1934].

When examining clinical benefit, patients with a best overall response assessment of unknown (UNK) will not be regarded as “responders” but may be included in the denominator for CBR calculation.

- **Phase II**

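### The SAP scores 24-week clinical benefit from any single non-progressing scan in the first 24 weeks, although the protocol requires SD or NCRNPD at week 24

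*SAP*

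**What the plan says.** Protocol Table 3-2 (section 3.2) defines the Phase II primary endpoint as the proportion with CR or PR, "or with stable disease (SD) at 24 weeks as per RECIST 1.1 or Non-CR Non-PD (NCRNPD) at week 24". For Phase I, Protocol Table 3-1 (section 3.1) is stricter still: disease control counts only if "NCRNPD) lasting 24 weeks or longer".

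SAP 3.5.1.2 agrees on timing: "The primary end point of this Phase II part of this trial, is CBR at week 24". The first sentence of SAP 3.5.2.2 also places the status at 24 weeks. Its second sentence, offered as a consequence of the first, accepts "any instance of CR, PR, SD or NCRNPD in the first 24 weeks of the treatment, without having an instance of progressive disease (PD"), and adds that unconfirmed CR and PR count. SAP 3.7.2.1 repeats this for Phase I: "any instance of CR, PR, SD or NCRNPD in the first 24 weeks of the treatment, without having an instance of PD".

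SAP 3.5.3, on missing values and discontinuations for the primary endpoint, is marked not applicable. SAP section 5 lists no change to the protocol analyses.

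**The concern.** The two adjacent sentences of SAP 3.5.2.2 are different rules. Status at week 24 needs evidence at week 24. Any instance within 24 weeks needs one scan, which on the 8-weekly schedule can be the week-8 scan, and then only the absence of recorded progression. A patient with SD at week 8 or 16 who withdraws consent, is lost or dies without imaged progression fails the first rule and passes the second. The second reads as the derivation and is the one likely to be programmed.

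For these early leavers the rule can only add successes. The trial is open-label and single-arm, tested against a fixed 10%, so no comparator absorbs the error.

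The contradiction shown concerns SD and NCRNPD. Protocol Table 3-2 can be read as tying the 24-week condition to those two categories only, so whether an earlier CR or PR needs a week-24 assessment is open.

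**Working it through.** **Does another passage repair the rule?**

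- SAP 3.5.2.2: "All the other patients will be counted as not having clinical benefit". This reaches only patients whom the preceding sentence has not already counted.
- SAP 3.5.2.2, unknown best response: one SD more than 6 weeks after the start gives a best overall response of SD (SAP 3.3.1.6), so the patient is not unknown.
- SAP 3.3.1.3 makes non-responders of patients who discontinue without a confirmed response or give no response information at the end of treatment. It also classes as non-response "unconfirmed response of CR/PR or response of SD, PD". CBR counts SD and unconfirmed responses, so this section cannot be the CBR rule.
- SAP Table 3-4 defines a week-24 window, "142, 198] days; (20, 28] weeks", but nothing ties CBR to it.
- SAP 3.7.3 says missing data are not imputed. It does not say how a patient with no week-24 scan is scored.

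None repairs it.

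**The plan's own figures.** Inputs from Protocol 10.4.2 and SAP section 4: null 10%, alternative 30%, 33 patients per group, success at 8 or more. From SAP 3.5.2.2: up to 10 or more if about 44 to 46 are enrolled. SAP section 4 reports 46 in group 1 and 33 in group 2. Exact binomial tails:

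| Rule | P(success), true 10% | P(success), true 30% |
|---|---|---|
| 8 or more of 33 | 1.41% | 81.8% |
| 10 or more of 46 | 1.40% | 92.1% |

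This agrees with the stated 80% power. Clopper-Pearson 95% lower limits: 7/33 0.0898, 8/33 0.1109; 9/46 0.0936, 10/46 0.1095. One patient moves either group across 0.10.

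**Size of the miscount.** Assumptions: the 10% dropout in SAP section 4 is taken as loss without progression by week 24 (the SAP gives it only as inflation for non-evaluable patients); loss and PFS are exponential; scans fall at weeks 8, 16 and 24; no leaver is scanned again.

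With true 24-week rate p and loss L, let S(t) = p^(t/24) and G(t) = (1−L)^(t/24). For p = 0.10 and L = 0.10:

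- S(8) = 0.4642, S(16) = 0.2154, S(24) = 0.10
- G(8) = 0.9655, G(16) = 0.9322, G(24) = 0.90
- Counted by both rules: A = G(24)·S(24) = 0.0900
- Counted only by the any-instance rule: B = [G(8)−G(16)]·S(8) + [G(16)−G(24)]·S(16) = 0.0155 + 0.0069 = 0.0224
- Counted rate: A + B = 0.1124

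Expected leavers counted without week-24 evidence: 33 × 0.0224 = 0.7 and 46 × 0.0224 = 1.0.

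If half of the leavers are still scanned, the counted rate is A + 0.5·(1−G(24))·S(24) + 0.5·B = 0.0900 + 0.0050 + 0.0112 = 0.1062.

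| Scenario, true rate 10% | Counted | False success, 8/33 | False success, 10/46 |
|---|---|---|---|
| Every patient scored correctly | 10.0% | 1.4% | 1.4% |
| 10% loss, half still scanned | 10.6% | 2.0% | 2.1% |
| 10% loss, none scanned | 11.2% | 2.7% | 2.9% |
| 10% loss, none scanned, Weibull PFS shape 0.7 | 10.7% | 2.1% | 2.2% |
| 10% loss, none scanned, Weibull PFS shape 1.5 | 12.1% | 3.9% | 4.5% |
| 5% loss, none scanned | 10.6% | 2.0% | 2.1% |
| 20% loss, none scanned | 12.4% | 4.5% | 5.3% |

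False success passes 2.5% at about 9% (n = 33) or 8% (n = 46) unscanned loss, and 5% at about 22% or 19%. Deaths without imaged progression are outside these figures: S(t) is PFS, so every death is a failure under both rules here, whereas the SAP sentence would count some as successes.

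**The case against.** The strongest defence is that the effect is small and that the protocol limits it. Scans continue every 8 weeks after treatment stops for reasons other than progression (Protocol 7.1.7), even after new therapy (Table 7-2), and an end-of-treatment scan is required unless one was done within 21 days (7.2.1.1). Stopping treatment alone should therefore not create the problem; withdrawal of consent, loss to follow-up or death must intervene. The no-later-scan case also spends the whole dropout allowance on such loss. This stands, and it is why the half-scanned figures matter. It does not make the two rules the same.

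A second defence also stands in part. At a true 30% with 10% unscanned loss, the any-instance rule counts 30.7% and the week-24 rule 27.0%, so the looser rule is nearer the truth there. A reader might cite how often the two rules reach different verdicts (16% and 20% of trials at a true 20%, 14% and 10% at a true 30%, for 33 and 46 patients) as evidence of harm. It is not: the null is false at those rates, and the SAP rule is then rejecting correctly. At a true 10% the two rules differ in only 1.9% and 2.3% of trials.

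A reader might also add the full 10% dropout to the 10% null and infer false success of 33% (8/33) or 44% (10/46). The documents give no basis for that. It needs every dropout to be a patient with an early SD who would otherwise have failed. Under the assumptions above, even a counted rate of 15% needs about 45% unscanned loss.

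**Conclusion.** The concern holds as a should-fix correction to the primary endpoint derivation. Followed literally, SAP 3.5.2.2 counts patients whom Protocol Table 3-2 does not, and SAP 3.7.2.1 does the same against the stricter Phase I wording. The departure is undeclared.

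The expected bias is modest. With 10% loss and no later scans, false success is just above the 2.5% implied by the 95% interval rule and below one-sided 5% (the printed alpha of 0.05% is read as 5%). With half of the leavers scanned it is below both. These results rest on the assumed loss rate and distributions, and they omit deaths without imaged progression. The reason to act is that a verdict resting on one patient should not depend on which of two adjacent sentences is programmed. A claim of grossly inflated error is not supported.

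**What to change.** In SAP 3.5.2.2 and 3.7.2.1, replace the any-instance sentence with:

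> Clinical benefit is CR, PR (confirmed or not), SD or NCRNPD documented at the scheduled week-24 assessment (week 24 ± 1 week) or, if that assessment is missing or was done earlier, at a later adequate assessment, with no PD or death recorded before that assessment or up to day 169, whichever is later. FAS patients without such an assessment count as no benefit and stay in the denominator.

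The window in SAP Table 3-4 should not be used for this: it opens at day 143 (143/7 = week 20.4), so a scan more than three weeks early could stand as 24-week benefit.

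In addition:

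- For Phase I, word the rule to meet the duration of at least 24 weeks in Protocol Table 3-1.
- Put the rule in SAP 3.5.3 in place of not applicable, and note in SAP 3.7.3 that counting missing as no benefit applies to CBR.
- Reconcile the sentence in SAP 3.5.2.2 and 3.7.2.1 that admits patients with only non-measurable disease to the numerator if they reach CR with the protocol's counting of NCRNPD.
- State whether a CR or PR before week 24 needs a week-24 assessment, and how scans after new anticancer therapy count for CBR. SAP 3.3.1.6 covers that only for best overall response.
- Show the any-instance rule only as a labelled sensitivity analysis.

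The cost is SAP text and one derivation, with no new data. Counting missing as no benefit is conservative. With 10% wholly unscanned loss, power at a true 30% is 70% (8/33) and 83% (10/46) instead of 82% and 92%. If half of the leavers are scanned it is 76% and 88%, so obtaining the follow-up scans the protocol already requires recovers part of the loss.
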